2.4 Primary Study Hypotheses

2.4.1 Primary Safety Hypothesis

The primary safety hypothesis is that the rate of Major Complications in the Primary Analysis Cohort (the proportion of subjects with one or more Major Complications as defined in Section 2.5.1 below) within 30 days of the procedure is less than the Performance Goal of 19.9%. This Performance Goal was derived from data in the published literature on the use of single or multiple Proglide/Prostar devices in large-bore procedures and from the clinical judgment of expert advisors.

Null hypothesis: The rate of Major Complications within 30 days of the procedure is not less than the Performance Goal of 19.9%.

$$H_0: \pi \geq 0.199$$

Alternative hypothesis: The rate of Major Complications within 30 days of the procedure is less than the Performance Goal of 19.9%.

$H_A: \pi < 0.199$,

where π is the population Major Complication rate. The rate of Major Complications in subjects treated with the MANTA device within 30 days will be presented along with the exact one-sided upper 97.5% confidence bound. If this upper confidence bound is less than 19.9%, the study will have met its primary safety objective.

If more than 13 of the subjects in the Primary Analysis Cohort (5% of the 250 assumed to achieve statistical power) are lost to follow-up or die due to a reason other than a Major Complication, the Major Complication rate will also be estimated from a Kaplan-Meier rate statistical curve. Subjects lost to follow-up will be censored at the date of their last contact. Subjects who die due to a reason other than a Major Complication will be censored at their date of death. An asymptotic one-sided upper 97.5% confidence bound will be placed on the estimated major complication rate at 30 days using the estimated survival curve and the standard error formula given by Peto, Peto, and Armitage¹ in Statistical Note 6. If this upper confidence bound is less than 19.9%, the study will have met its primary safety objective.

In addition, the proportion of subjects with each individual Major Complication will be presented along with their two-sided exact 95% confidence intervals.

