3 DETERMINATION OF SAMPLE SIZE

The sample size for this study was based on the primary effectiveness and safety endpoints of Time to Hemostasis and major complication rate. The population Time to Hemostasis is assumed to be 6 minutes, with a standard deviation of 11 minutes. Based on these assumptions and a normal distribution, 62 subjects will provide 80% power to reject the primary effectiveness hypothesis at a one-sided significance of 0.025.

The population Major Complication rate is assumed to be 13%. Based on this assumption, 250 subjects will provide 80% power to reject the primary safety hypothesis at a one-sided significance of 0.025. Therefore, the necessary sample size is driven by the primary safety endpoint and is 250 subjects.

Assuming a lost to follow-up rate of approximately 5%, the study will treat a total of 263 subjects to ensure an adequate sample size of 250 subjects meeting the 30-day primary safety endpoint.

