5 DATA CONVENTIONS AND DEFINITIONS

5.1 Handling of Missing Data

Missing data will not be imputed for safety endpoints. However, if more than 13 subjects in the Primary Analysis Cohort either die for a reason other than a Major Complication or are lost to follow up within 30 days of treatment, then the rate of Major Complications will also be estimated by the Kaplan-Meier method, to allow for subjects who are censored before a Major Complication can be observed. See Section 2.4.1 for further details.

For effectiveness endpoints, it is highly unlikely that there will be missing data for Time to Hemostasis, Technical Success, Ambulation Success, Time to Ambulation, Treatment Success or Procedure Time. However, if any of these data are missing (i.e., in the event that Time to Hemostasis cannot be evaluated because a surgical repair must be performed), the worst value observed for any subject at the same study site within each analysis cohort, will be imputed for the missing value. Missing data for a subject in the Primary Analysis Cohort will be imputed with the worst value observed for any Primary Analysis Cohort subject at the same study site, and missing data for a subject in the Roll-In Cohort will be imputed with the worst value observed for any roll-in subject at the same study site.

No other imputations will be carried out for missing data.

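### The Kaplan-Meier safety bound has no stated scale: computed linearly, its one-sided error is above 2.5% (3.1% at N=263, 3.4% at N=250, without early censoring), and its trigger lacks the 30-day limit of SAP 5.1

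*SAP*

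**What the plan says.** The primary safety test compares the 30-day Major Complication rate with a Performance Goal of 19.9%. SAP section 3 sizes it for a true rate of 13%: "250 subjects will provide 80% power to reject the primary safety hypothesis at a one-sided significance of 0.025", and "the study will treat a total of 263 subjects" to allow for about 5% loss.

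Under SAP 2.4.1 the crude rate "will be presented along with the exact one-sided upper 97.5% confidence bound". If more than 13 subjects are lost or die of another cause, a Kaplan-Meier rate is estimated as well: "An asymptotic one-sided upper 97.5% confidence bound will be placed on the estimated major complication rate at 30 days using the estimated survival curve" and a standard error formula given by citation. A Kaplan-Meier bound below 19.9% also meets the objective. No transformation is named, and nothing says which bound governs when both are computed.

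SAP 6.3.2 and Protocol 8.3.3 describe the same Kaplan-Meier bound, with the same citation and pass rule, as exact.

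The trigger is also worded differently. SAP 5.1 counts subjects who "either die for a reason other than a Major Complication or are lost to follow up within 30 days of treatment". SAP 2.4.1 and 6.3.2 give no time limit, while follow-up runs to 60 ± 14 days.

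**The concern.** A bound made from an estimate and a standard error, with no scale named, would ordinarily be programmed as rate + 1.96 x SE. That SE is evaluated at the observed rate, which in a passing trial lies well below 19.9%. It is therefore smaller than the SE that applies at the Performance Goal, and the bound sits too low. The error favours the device, on a bound that can settle the primary safety objective at a stated one-sided 0.025.

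The open-ended trigger adds to this. Deaths or losses after day 30 do not affect the 30-day Kaplan-Meier estimate, yet they could open a second and looser route to success.

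**Working it through.** **Inputs.** Performance Goal 19.9% (SAP 2.4.1). True rate 13%, one-sided 0.025, 80% power, N=250, 263 treated (SAP section 3). Trigger of more than 13 subjects (SAP 2.4.1, 5.1). EU deaths 4 of 50 (Protocol 1.4).

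**The plan's own figure.** With an exact binomial upper bound, N=250 passes with at most 37 events. P(X ≤ 37 | 250, 0.199) = 2.32% and P(X ≤ 37 | 250, 0.13) = 82.7%. The stated 250 for 80% power is reproduced.

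**No censoring before day 30.** Any Kaplan-Meier SE then equals √(p(1−p)/n), so no assumption about the cited formula is needed. The linear scale is still an assumption.

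- Linear: p + 1.96·SE. For 40/263, p = 0.1521 and SE = √(0.1521 × 0.8479/263) = 0.0221, so the bound is 0.1521 + 1.96 × 0.0221 = 19.55%: pass. At the Performance Goal the SE would be √(0.199 × 0.801/263) = 0.0246.
- Exact (Clopper-Pearson): 40/263 gives 20.13% (fail); 39/263 gives 19.71% (pass).
- Complementary log-log: 1 − exp(−exp(θ + 1.96τ)), with S = 1 − p, θ = ln(−ln S) and τ = SE/(S·|ln S|). 40/263 gives 20.15% (fail); 39/263 gives 19.73% (pass).

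The one-sided error is the binomial probability of passing at a true 19.9%:

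| Bound | N=263: most events that pass | Error | N=250: most events that pass | Error |
|---|---|---|---|---|
| Exact | 39 | 2.09% | 37 | 2.32% |
| Complementary log-log | 39 | 2.09% | 37 | 2.32% |
| Linear | 40 | 3.08% | 38 | 3.42% |
| Log-survival | 41 | 4.41% | 38 | 3.42% |

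Over every N from 250 to 263 the linear error runs from 2.9% to 4.1%. The log-log error stays below 2.5% throughout.

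**With early censoring.** This requires an assumed SE, taken as S·√((1−S)/R) with R the number at risk at day 30, and assumed timing: censoring uniform over 30 days and most events in the first two days.

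- At N=263, simulated error of the linear bound was 3.0 to 3.4% with 18 subjects assigned to be censored, 2.7% with 26 and 2.6% with 40. Among those trials in the 18-subject setting that actually met the trigger, it was 3.3 to 3.9%.
- A second set of simulations with 14 to 26 censored gave 2.7 to 3.4% at N=263 and 2.7 to 3.5% at N=250. Log-log bounds in these settings gave about 1.8 to 2.3%.
- The outcome for 40 events of 263 depends on timing. With all censoring after the events, the linear bound is 19.69% with 14 censored (pass), 19.83% with 26 (pass) and 20.00% with 40 (fail). With 14 censored before the events it is 20.63% (fail).

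**Trigger.** Without a 30-day limit, deaths up to about day 60 count. P(more than 13 of 263) is 17% at 4% mortality, 44% at 5%, 71% at 6% and 96% at the 8% seen in the EU study. The exact 95% interval for 4 of 50 is 2.2% to 19.2%. If late deaths open the route and there is little early censoring, the no-censoring figures apply almost unchanged.

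**The case against.** The strongest reply is that the linear form is not in the documents. SAP 2.4.1 gives no scale, no multiplier and no written formula, and a log-log bound is just as asymptotic and would hold the level. That stands. A reader might infer that the SAP prescribes a bound that breaks its error rate, but the documents support only the conditional statement. Nor can the point be separated from the wording conflict, since two of the three descriptions say exact. That label does not settle the matter, however, because a standard error does not by itself give an exact bound.

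A reader might also infer that 40 of 263 events would pass. That holds without early censoring; with it, the result can go either way. The gap is about one event, the crude rate keeps its exact bound, and an openly asymptotic bound claims only nominal coverage. All of this limits the size of the problem without removing it, because the bound is given power to decide the primary objective.

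On the trigger, 5.1 refers back to 2.4.1, and the 5% allowance concerns loss before the 30-day endpoint, so a 30-day window is probably intended. A reader might take the 96% as a forecast, but four deaths cannot support one. The wording in 2.4.1 and 6.3.2 still permits the wider count.

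**Conclusion.** The concern holds in conditional form. The scale and formula of a bound that can decide the primary safety objective are not stated, and the sections disagree on whether it is exact or asymptotic. On the ordinary linear reading its one-sided error exceeds 2.5%: 3.1% at N=263 and 3.4% at N=250 without early censoring, and roughly 2.6 to 3.5% over the simulated settings with early censoring, depending on its amount and timing. A complementary log-log bound stays at about 1.8 to 2.3%. The difference is about one event: 40 against 39 of 263, or 38 against 37 of 250, without early censoring.

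The no-censoring figures rest only on the linear scale. The censored figures rest also on an assumed SE formula and assumed timing. The missing 30-day limit in 2.4.1 and 6.3.2 follows from the text alone; how often it would matter depends on a mortality that the documents estimate very imprecisely. The point should be corrected, but it does not undermine the design.

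**What to change.** In SAP 2.4.1 and 6.3.2:

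- Specify a single upper 97.5% bound for the 30-day Kaplan-Meier rate, computed on the complementary log-log scale with Greenwood variance and back-transformed. Replace the conflicting asymptotic and exact labels to match.
- Add to the trigger the 30-day limit that 5.1 already uses.
- Record the new bound in SAP section 8, which now lists no changes, as a departure from Protocol 8.3.3.

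The cost is a slightly less favourable bound, about one event. Without early censoring the limit moves from 40 to 39 of 263, and power at a true 13% goes from 87.5% to 83.5%, still above the planned 80%. The other cost is a documented departure from the formula that the protocol cites. If the sponsor prefers to amend Protocol 8.3.3 instead, Protocol 14.1 requires the full approval process.

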2.4.2 Primary Effectiveness Hypothesis

The primary effectiveness hypothesis is that population mean Time to Hemostasis in the Primary Analysis Cohort is less than the Performance Goal of 10 minutes. This Performance Goal was derived from data in the published literature on the use of single or multiple Proglide/Prostar devices in large-bore procedures and from the clinical judgment of expert advisors.

Null hypothesis: The mean Time to Hemostasis in the study is not less than the Performance Goal of 10 minutes.

$H_0: \mu \geq 10$

Alternative hypothesis: The mean Time to Hemostasis in the study is less than the Performance Goal of 10 minutes.

$H_A: \mu < 10$

where μ is the population mean Time to Hemostasis. The mean Time to Hemostasis will be presented along with the exact one-sided upper 97.5% confidence bound. If this upper confidence bound is less than 10 minutes, the study will have met its primary effectiveness objective.

¹ Peto R, Pike MC, Armitage P, et al. Design and analysis of randomized clinical trials requiring prolonged observation of each patient. II. analysis and examples. *British Journal of Cancer*. 1997;35(1):1-39.

2.5 Safety Assessments

The primary and secondary safety analyses will be performed on the Safety population, defined as all enrolled study subjects in the Primary Analysis Cohort in whom an attempt to use the device is made (use of the puncture locating dilator prior to assessment of intra-procedure exclusions is not considered an attempted use of the device). Roll-in subjects will be summarized separately and will not be analyzed against the safety Performance Goal or Clinical Acceptance Criterion.

All adverse events will be MedDRA coded and will be presented by Preferred Term and System Organ Class. The Clinical Events Committee (CEC) will review and adjudicate certain adverse events, as defined in the protocol, and determine whether an event is a Major Complication, Minor Complication, or VARC-2 Major Vascular Complication for the primary and secondary safety endpoints.

2.5.1 Primary Safety Variable

The primary safety endpoint is the percentage of subjects with one or more Major Complications listed below within 30 days of the procedure. Major Complications include the following events:

Major Complications:

- i. Vascular injury attributable to the MANTA device requiring surgical repair or stent-graft;
- ii. Access site-related bleeding that is attributable to failure of or sub-optimal performance of the MANTA device and that results in transfusion;
- iii. New onset ipsilateral lower extremity ischemia that originates with the common femoral artery, is attributable to the MANTA device, causes a threat to the viability of the limb, and requires surgical repair or additional percutaneous intervention;
- iv. Access site-related nerve injury attributable to the MANTA device that is permanent (lasting >30 days) or requires surgical repair; and
- v. Access site-related infection requiring intravenous antibiotics and/or extended hospitalization.

2.5.2 Secondary Safety Variables

The secondary safety endpoints include:

1. The percentage of subjects with one or more Minor Complications within 30 days of the procedure;
2. The percentage of subjects with one or more VARC-2 Major Vascular Complications within 30 days of the procedure.

Minor Complications will be qualitatively, but not statistically, assessed against a Clinical Acceptance Criterion of 20% as derived from data in the published literature on the use of single or multiple Proglide/Prostar devices in large-bore procedures and from the clinical judgment of expert advisors. This CAC will not be statistically tested. VARC-2 Major Vascular Complications will not be statistically tested against a PG or qualitatively assessed against a CAC.

Minor Complications:

- i. Non-treated pseudoaneurysm attributable to the MANTA device and documented by ultrasound;
- ii. Non-treated or treated arteriovenous (AV) fistula attributable to the MANTA device and documented by ultrasound;
- iii. Pseudoaneurysm treated with ultrasound-guided compression, ultrasound-guided thrombin injection or ultrasound-guided fibrin adhesive injection;
- iv. Access site hematoma that is attributable to failure of or sub-optimal performance of the MANTA device, is ≥ 10 cm and is confirmed by ultrasound;
- v. Late (following hospital discharge) access site-related bleeding;
- vi. Ipsilateral lower extremity arterial emboli attributable to the MANTA device;
- vii. Ipsilateral vein thrombosis attributable to the MANTA device;
- viii. Transient access site-related nerve injury;
- ix. Access site wound dehiscence; and
- x. Localized access site infection treated with intramuscular or oral antibiotics.

Major Vascular Complications: Adapted² from the VARC-2 Clinical Guidelines³:

- i. Access site or access-related vascular injury (dissection, stenosis, perforation, rupture, arterio-venous fistula, pseudoaneurysm, hematoma, irreversible nerve injury, compartment syndrome, percutaneous closure device failure) leading to death, life threatening or major bleeding, visceral ischemia, or neurological impairment OR
- ii. Distal embolization (noncerebral) from a vascular source requiring surgery or resulting in amputation or irreversible end-organ damage OR
- iii. The use of unplanned endovascular or surgical intervention associated with death, major bleeding, visceral ischemia or neurological impairment OR
- iv. Any new ipsilateral lower extremity ischemia documented by patient symptoms, physical exam, and/or decreased or absent blood flow on lower extremity angiogram OR
- v. Surgery for access site-related nerve injury OR
- vi. Permanent access site-related nerve injury.

In addition to the pre-determined categories of Major Complications, Minor Complications, and VARC-2 Major Vascular Complications, all adverse events recorded throughout the entire 60-day duration of the study will be categorized and summarized descriptively by type, severity, and relationship to device/procedure. Serious Adverse Events (SAEs) and Unanticipated Adverse Device Effects (UADEs) will also be summarized. Adverse events will not be statistically tested against a PG or qualitatively assessed against a CAC.

2.6 Effectiveness Assessments

The primary and secondary effectiveness analyses will be performed on both the Primary Analysis Cohort population and the Per Protocol population. Roll-in subjects will be summarized separately

² The Major Vascular Complications definition from the VARC-2 guidelines was adapted as follows: The first bullet of the definition ("Any aortic dissection, aortic rupture, annulus rupture, left ventricle perforation, or new apical aneurysm/pseudoaneurysm OR") was deleted from the definition used in this protocol, as these adverse events are entirely unrelated to the femoral access site.

³ Kappetein AP, Head SJ, Génereux P et al. Updated standardized endpoint definitions for transcatheter aortic valve implantation: The Valve Academic Research Consortium-2 consensus document. J Thorac Cardiovasc Surg 2013;145:6-23.

from the Primary Analysis Cohort and will not be tested against the effectiveness Performance Goal.

2.6.1 Primary Effectiveness Variable

The primary effectiveness endpoint is the mean Time to Hemostasis, defined as the elapsed time between MANTA deployment (withdrawal of sheath from artery) and first observed and confirmed arterial hemostasis (no or minimal subcutaneous oozing and the absence of expanding or developing hematoma).

2.6.2 Secondary Effectiveness Variables

The secondary endpoints include:

1. Proportion of subjects with Technical Success
2. Proportion of subjects with Ambulation Success
3. Proportion of subjects with Treatment Success
4. Mean Time to Ambulation
5. Mean Procedure Time

These secondary endpoints are defined in Section 6.2.2.

2.7 Additional Endpoints

Not applicable.

2.8 Other Variables

2.8.1 Subject Characteristics

The following subject characteristics will be collected and analysis will be performed on both the Primary Analysis Cohort population and the Per Protocol population. Roll-in subjects will be summarized separately from the Primary Analysis Cohort. All analysis populations will also be summarized by endovascular procedure type.

- Subject disposition
- Protocol deviations and other reasons for exclusion from analysis sets
- Demographic variables will include:
 - Age
 - Age Category (<65, 65-79, and 80+ years)
 - Gender
 - Race
 - Ethnicity
 - Height
 - Weight
 - BMI

- Other baseline characteristic variables will include:
 - Prior surgical history events of interest
 - Baseline laboratory results of interest
 - Anti-coagulant and anti-platelet concomitant medications at baseline and during procedure

The following data will be provided as by-subject listings:

- Discontinued subjects
- Protocol deviations
- Subjects excluded from the per protocol set
- Demographics, including STS cardiac surgery risk score (TAVI subjects only)
- Medical and surgical history
- Concomitant medications
- Procedural and discharge data
- Device deficiencies
- Effectiveness data
- Adverse events
- Baseline laboratory results
- Clinical examination results
- Pregnancy test results
- Ipsilateral Ankle-brachial Index results
- Ultrasound results

2.8.2 Procedural and Discharge Data

The following data will be collected during the procedure and discharge and analysis will be performed on both the Safety Evaluation Set and the Per Protocol population. A separate analysis will also be performed for the Roll-in subjects.

1. Endovascular procedure type
2. Procedure sheath brand
3. Procedure sheath size (F)
4. Index device manufacturer/brand
5. Index device size (mm)
6. Effective puncture size (F)
7. MANTA size (14F or 18F)
8. Target artery (left or right)
9. Target artery diameter (mm)
10. Sheath to femoral artery ratio (SFAR)
11. Pre-deployment ACT (sec)
12. Use of adjunctive methods to obtain hemostasis
13. Use of adjunctive methods for treating oozing
14. Any thrombus observed on the MANTA components (Y/N)
15. Post-deployment angiogram results

- 16. Time to discharge post-MANTA deployment
- 17. Time to discharge post-ambulation
- 18. Mean ABI scores at baseline, pre-procedure, post-procedure, discharge, follow-up
- 19. Ultrasound findings post-procedure and at follow-up
- 20. Device deficiencies

Other procedure data will be reported in by-subject listings. Definitions for these data points are provided in Section 6.2.3.

2.8.3 *Exploratory Analyses*

Additional exploratory analyses will be performed as needed.

3 DETERMINATION OF SAMPLE SIZE

The sample size for this study was based on the primary effectiveness and safety endpoints of Time to Hemostasis and major complication rate. The population Time to Hemostasis is assumed to be 6 minutes, with a standard deviation of 11 minutes. Based on these assumptions and a normal distribution, 62 subjects will provide 80% power to reject the primary effectiveness hypothesis at a one-sided significance of 0.025.

The population Major Complication rate is assumed to be 13%. Based on this assumption, 250 subjects will provide 80% power to reject the primary safety hypothesis at a one-sided significance of 0.025. Therefore, the necessary sample size is driven by the primary safety endpoint and is 250 subjects.

Assuming a lost to follow-up rate of approximately 5%, the study will treat a total of 263 subjects to ensure an adequate sample size of 250 subjects meeting the 30-day primary safety endpoint.

